Prior and concomitant therapies not permitted in this study are listed in Section 5.2, exclusion criteria. Therapies listed in the exclusion criteria are also prohibited during the study (exception: TCSs and TCIs may only be used as rescue medication).

In addition, the use of antihistamines and live vaccination are not allowed during the study.

If the participant took a prohibited medication or used a prohibited non-drug therapy for any reason, the investigator should consult with the sponsor to determine if the participant should be withdrawn from study intervention and/or the study.

For the purpose of efficacy analysis, participants receiving any pharmacologically active nonstudy medication or phototherapy for AD will be considered as treatment failures after the start of such medication, except for the use of defined topical rescue medication up to/including Week 8. Whenever possible, efficacy and safety assessments according to Visit 7 (EOT) should be conducted immediately before administering any systemic medications for AD or initiation of phototherapy (= SoC). For zabedosertib, a wash-out period of 7 days (approximately 5 half-lives) is recommended, because there is no experience or data with a combination of zabedosertib and systemic AD treatment.

SoC should be reserved for participants who do not respond adequately to topical treatment (at least 7 days of use). If a participant receives SoC treatment with systemic corticosteroids or non-steroidal systemic immunosuppressive drugs (cyclosporine, methotrexate, MMF, azathioprine, baricitinib etc.) dupilumab, tralokinumab or initiation of phototherapy, study intervention has to be discontinued and EOT assessments including FU visits performed.

7 Discontinuation of Study Intervention and Participant Discontinuation/Withdrawal

Discontinuation of specific sites or of the study as a whole are detailed in Appendix 1 (Section 10.1.11).

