7.1 Discontinuation of Study Intervention

In rare instances, it may be necessary for a participant to permanently discontinue study intervention. If study intervention is permanently discontinued, the participant should, if at all possible, remain in the study to be evaluated for EOT and FU assessments, as described at the end of this section. See the SoA (see Section 1.3) for data to be collected at the time of discontinuation of study intervention and FU and for any further evaluations that need to be completed.

If an exclusion criterion is met during the study, the investigator should consider discontinuation of the participant's study intervention, if medically indicated.

The participant's study intervention must be permanently discontinued, if anything of the following occurs:

- Pregnancy (see also Section 8.4.5).
- Participant receives SoC treatment with systemic corticosteroids or non-steroidal systemic immunosuppressive drugs or phototherapy (see also Section 6.9.3).
- Participant interrupts study intervention for more than 10 consecutive days (see also Section 7.1.4).
- Participant experiences an AE which is considered to be related to study treatment or study procedure and, in the investigator's judgment, is severe enough in nature to warrant treatment discontinuation. Common Terminology Criteria for AEs (CTCAE) current version, Grade 3 or higher (may be used as guidance).
- Any malignancy.
- Febrile illness for more than 48 hours and clinical or biochemical signs of infection (e.g., clinically relevant abnormality of hsCRP level).
- Participants who received COVID-19 vaccine during the study treatment phase, must be withdrawn from the study. An interval of at least 14 days between the last study drug and the vaccine dose is recommended.
- Positive SARS-CoV-2 viral RNA test or clinical evidence for COVID-19 during the study despite a negative test result (study intervention should be interrupted until test results are available). Testing during the study should be done on an individual basis as medically indicated according to local practice, triggered by signs and symptoms of a potential SARS-CoV-2 infection or contact history. If current COVID-19 infection is confirmed, the participant must be permanently discontinued from study intervention.
- The participant's randomized treatment assignment is unblinded by the investigator or treating physician.

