- Agents for dermatitis, excluding corticosteroids (as listed below) (D11AH, only systemic as listed below)
 - Dupilumab (IL-4 and IL-13 antibody) (D11AH05),
 - Tralokinumab (IL-13 antibody) (D11AH07),

Topical AD medication (route of administration: topical, cutaneous)

Corticosteroids for topical use (plain or combination with antiseptics/antibiotics/other)

- Corticosteroids, weak (group I) (D07AA, D07BA, D07CA, D07XA)
- Corticosteroids, moderate (group II) (D07AB, D07BB, D07CB, D07XB),
- Corticosteroids, potent (group III) (D07AC, D07BC, D07CC, D07XC),
- Corticosteroids, very potent (group IV) (D07AD, D07BD, D07CD, D07XD)
- Agents for dermatitis, excluding corticosteroids (as listed below) (D11AH, only topical as listed below)
 - Calcineurin inhibitors (D11AH01, D11AH02),
 - Cromoglicic acid (D11AH03),
 - Crisaborole (PDE4 inhibitor) (D11AH06),
 - Ruxolitinib (JAK inhibitor) (D11AH09)

In case of multiple possible potency groups for corticosteroids the highest possible potency will be considered.

Medication will be considered as AD medication if the indication for use is

- "rescue treatment: protocol specified"
- or if the indication is
- "treatment of atopic dermatitis related symptoms"

or if the indication is

• "adverse event" and the adverse event is consistent with the indication AD Adverse events will be classified as consistent with AD or not during blind data review by persons without access to any individual post-dose efficacy data. The following AEs will always be considered to be consistant with AD:

- PT: Dermatitis atopic,
- PT: Neurodermatitis,
- PT: Eczema.

Frequencies will be presented for each category and all subcategories.

Furthermore, a frequency table will be presented for relevant prior, concomitant and posterior procedures (other than those scheduled in the protocol). For posterior procedures only participants will be considered who completed the follow-up period.

For procedures the following definitions apply:

- Prior procedure: Procedure applied before start of the study intervention intake (only prior procedures within 6 months (i.e. 183 days) before treatment start will be considered),
- Concomitant procedure: Procedure applied during treatment period, i. e. between first and last study intervention intake,
- Posterior procedure: Procedure applied after end of treatment.

7. References

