If rescue medication is given for indication not consistent with AD this might also affect AD related efficacy scores. Thus, efficacy values assessed after rescue medication use at or after Day 56 (Visit 6) (or Day x (Visit x) for supplementary analyses) will be set to missing and the missing values will be imputed as described for the intercurrent event "discontinuation of study intervention due to other reasons".

Identification of intercurrent event "use of systemic standard of care"

All medication on the concomitant medication page that is systemic standard of care according to the protocol and was used at or after treatment start will be identified:

- systemic corticosteroids,
- non-steroidal systemic immunosuppressive drugs (cyclosporine, methotrexate, MMF, azathioprine, baricitinib etc.),
- dupilumab,
- tralokinumab,
- phototherapy.

Systemic SoC will be identified by the following ATC codes if route of administration is oral, intramuscular, subcutaneous or intravenous:

- H02AB/H02BX Glucocorticoids for systemic use
- L04AD: Calcineurin-inhibitors
 - L04AD 01 Ciclosporin
 - L04AD 02 Tacrolimus
 - L04AD 03 Voclosporin
- L04AA: selective immunosuppressants

- L04AA06 MMF (Mycophenolic acid, Mycophenolate sodium, Mycophenolate acid, Mycophenolate mofetil)

- L04AA37 JAK-inhibitor Baricitinib
- L04AA44 JAK-inhibitor Upadacitinib
- D11AH08 JAK-inhibitor Abrocitinib
- L04AX: other immunosuppressants
 - L04AX01 Purine antagonist Azathioprine
 - L04AX03, L01BA01 Antineoplastic folic acid analogues Methotrexate

- Page: 59 of 72
- D11AH05, IL-4 and IL-13 monoclonal antibody Dupilumab
- D11AH07 IL-13 antibodies Tralokinumab
- L04AC Interleukin inhibitors used as immunosuppressants
 L04AC IL-13 antibodies Lebrikizumab not approved
 L04AC IL-31 antibodies Nemolizumab not approved
- Phototherapy (Psoralens for systemic (D05BA) or topical (D05AD) use before/together with phototherapy (PUVA))

The occurrence of the intercurrent event "use of systemic standard of care" will be applicable if the indication for use for the therapies listed above is

• "Treatment of atopic dermatitis related symptoms"

or if indication is

- "Adverse event" and the adverse event is consistent with the indication AD (Adverse events will be classified as consistent with AD or not during blind data review by persons without access to any individual post-dose efficacy data. The following AEs will always be considered to be consistant with AD:
 - PT: Dermatitis atopic,

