 - PT: Neurodermatitis,
 - PT: Eczema).

If systemic standard of care medication is given for indication not consistent with AD this will also affect AD related efficacy scores. Thus, efficacy values assessed after systemic SoC use will be set to missing and the missing values will be imputed as described for the intercurrent event "discontinuation of study intervention due to other reasons".

Identification of intercurrent event "Discontinuation of study intervention due to lack of efficacy"

All reasons for treatment discontinuation will be reviewed. The occurrence of the intercurrent event "Discontinuation of treatment due to lack of efficacy" will be applicable if the underlying reason for discontinuation of treatment is

- "Adverse event" that reflects lack of efficacy (e.g. disease flare, worsening of AD) (Adverse events leading to discontinuation of treatment will be classified as reflecting lack of efficacy or not during blind data review by persons without access to any individual post-dose efficacy data. The following AEs will always be considered to reflect lack of efficacy)
 - PT: Dermatitis atopic with
 - LLT : Atopic dermatitis flare
 - LLT : Atopic flare-up
 - LLT : Dermatitis atopic aggravated
 - PT: Rebound atopic dermatitis
 - PT: Neurodermatitis with
 - LLT : Neurodermatitis aggravated

Page: 60 of 72

- PT: Eczema with
 - LLT : Eczema aggravated
 - LLT : Eczema exacerbated
 - LLT: Eczema
- PT: Rebound eczema

or if the reason is

• "Lack of efficacy" based on the investigator's assessment and there is no respective adverse event reported.

or if the reason is

• "Physician decision: switching to other therapy" This should be selected if any prohibited pharmacologically active non-study medication or phototherapy for AD is started and the study medication needs to be discontinued for this reason.

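### Within the systemic standard-of-care event, SAP 8.3 can recognise phototherapy only by a psoralen drug code, so phototherapy without a psoralen has no record-based route to non-response

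*SAP*

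**What the plan says.** **Protocol.** Section 6.9.3 equates SoC with "any systemic medications for AD or initiation of phototherapy (= SoC"), without limiting the type of phototherapy. For the efficacy analysis, participants receiving active non-study "medication or phototherapy for AD will be considered as treatment failures after the start of such medication". Section 7.1 lists this among the events that require permanent discontinuation: "Participant receives SoC treatment with systemic corticosteroids or non-steroidal systemic immunosuppressive drugs or phototherapy".

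**SAP, the SoC event.** Section 8.3 starts from "All medication on the concomitant medication page that is systemic standard of care according to the protocol" and names phototherapy in the general list that follows. The operational rule is then: "Systemic SoC will be identified by the following ATC codes if route of administration is oral, intramuscular, subcutaneous or intravenous". The phototherapy entry under that rule is "Phototherapy (Psoralens for systemic (D05BA) or topical (D05AD) use before/together with phototherapy (PUVA", where its brackets close.

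**SAP, the discontinuation event.** Also in 8.3, a stop recorded as the physician's decision to switch to another therapy counts as discontinuation for lack of efficacy, and so as non-response. On that reason the SAP says: "This should be selected if any prohibited pharmacologically active non-study medication or phototherapy for AD is started", where study medication has to stop on that account.

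**SAP, other places.** Section 8.4.1 sets efficacy values to missing after SoC, and defines SoC there by the medication list in 8.3. Section 6.3 says "a frequency table will be presented for relevant prior, concomitant and posterior procedures", but 8.3 does not use procedure records to identify any intercurrent event.

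**The concern.** The protocol's rule covers all phototherapy for AD. The SAP's search for it covers phototherapy given with a coded psoralen. Phototherapy without a psoralen (UVB is an example) is not a drug and has no code on the list. Topical psoralen is on the list, but under a route condition that a topical product cannot meet.

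Every other SoC therapy that the protocol names has a check that works from the medication record, independently of how the site codes the end of treatment. Phototherapy without a systemic psoralen depends on the site stopping study drug and choosing one particular reason.

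The primary endpoint is at stake. SAP 8.4.1 says that values after SoC are likely to look better and should stay out of the analysis. A missed case could leave such a value in and count as an EASI 75 responder. The same flag also feeds entry to the per-protocol and full analysis sets (SAP 3) and the life-table summaries (SAP 4.4.6). The biomarker-sample validity rule (SAP 4.4.8) relies on the same 8.3 medication lists.

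**Working it through.** **Step 1. Follow each type of case through the rules.**

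| Case | SoC event (8.3) | Discontinuation event (8.3) | Result in the primary analysis |
|---|---|---|---|
| PUVA with systemic psoralen, for AD | Caught by D05BA | Also caught if coded as planned | Non-responder |
| PUVA with topical psoralen, for AD | D05AD is listed, but the literal route filter excludes it | Caught if stopped and coded as planned | Depends on the stop and its coding |
| No psoralen; stops, coded as switching therapy | Not identified | Caught | Non-responder |
| No psoralen; stops, coded to a reason not classed as lack of efficacy | Not identified | Not caught | Stop before Day 56: excluded. Day 56 or later: imputed (SAP 1.1) |
| No psoralen; stays on study drug against Protocol 7.1 | Not identified | Not applicable | Day 84 EASI kept as observed; 8.4.1 does not set it to missing |

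The last row is the main gap and the row above it the smaller one. For both, Protocol 6.9.3 calls for treatment failure. A topical-psoralen case can fall into either if the filter is applied literally.

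**Step 2. Reproduce the plan's power figure.** Inputs from SAP 5: 38 and 19 evaluable, true rates 0.49 and 0.16, Beta(1,1) priors, success if the posterior probability exceeds 0.90. With k responders among n, each arm's posterior is Beta(k+1, n−k+1), and

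P(π_BAY > π_Plac | data) = ∫ f_BAY(x) · F_Plac(x) dx.

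Enumerating all 39 × 20 outcomes gives power of 91.0%, in line with the stated figure of at least 90%. The point does not depend on it.

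**Step 3. What one missed case can do.** One participant is 1/38 = 2.6 percentage points on zabedosertib or 1/19 = 5.3 points on placebo. The smallest zabedosertib counts that meet the criterion are 5, 8, 11, 13 and 15 of 38 for placebo counts 0, 1, 2, 3 and 4 of 19. The counts below are illustrative.

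| Zabedosertib | Placebo | Posterior | Criterion |
|---|---|---|---|
| 13/38 | 3/19 | 0.918 | met |
| 12/38 (one false responder removed) | 3/19 | 0.885 | not met |
| 11/38 | 2/19 | 0.931 | met |
| 11/38 | 3/19 (one false responder added) | 0.841 | not met |
| 19/38 | 3/19 | 0.994 | met |
| 18/38 | 3/19 | 0.990 | met |
| 19/38 | 4/19 | 0.981 | met |

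The planned rates correspond to 0.49 × 38 = 18.6 and 0.16 × 19 = 3.0 responders, so the last three rows are the planned region. There one case in either arm changes nothing. The threshold of 11 against 2/19 is itself very fine: 10/38 against 2/19 gives 0.89999. The Monte Carlo standard error of 100,000 independent draws is √(0.9 × 0.1 / 100,000) = 0.0009, so that outcome cannot be told apart from 0.90 by the planned simulation.

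The error can go either way: a missed case on zabedosertib favours the drug, one on placebo counts against it.

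**The case against.** The strongest reply is that SAP 8.3 does cover phototherapy. The switching-therapy reason names it, has no psoralen or route condition, and leads to non-response. Since the protocol requires study drug to stop, a participant handled and coded as directed is caught. This stands, so the defect belongs to the SoC event and not to 8.3 as a whole.

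A reader might also infer that anyone whose stop is coded otherwise keeps a post-phototherapy EASI. The documents do not support that in general. After an early stop only the end-of-treatment and follow-up visits remain. Follow-up values are not used in the Bayesian analysis (SAP 4.1.1). End-of-treatment values count only within a visit window and no later than three days after the last dose (SAP 8.4.1). Protocol 6.9.3 asks for those assessments before phototherapy starts, whenever possible. The usual outcome is a pre-phototherapy value, imputation or exclusion. SAP 1.1 and 4.2.2 also state that SoC begun after a stop for other reasons does not trigger non-response, so some of these participants lie outside the rule by design.

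It can further be said that the route conflict is a drafting slip, because the entry expressly lists topical use. The intent is indeed clear, but the two lines cannot both be programmed as written.

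Finally, that phototherapy would be recorded as a procedure is an inference. The case report form is not available, and 8.3 names phototherapy among items to be found on the medication page. Even there, however, an entry without a psoralen matches no code on the list.

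**Conclusion.** The point holds as a limited operational gap between the protocol's rule and the SAP's algorithm. Within the SoC event, phototherapy without a psoralen has no identifier, and topical psoralen is listed and filtered out at once. The main exposure is a participant who has such phototherapy and continues study drug against the protocol. The smaller one is a stop because of phototherapy coded to another reason, which ends in imputation or exclusion where the protocol calls for failure.

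It would be tempting to conclude that the non-responder rule fails for phototherapy altogether, or that the trial's result is in doubt. Neither follows: the discontinuation reason covers the expected course, and at the planned rates one case leaves the posterior at 0.98 or above. One case could reverse the decision only near the 90% boundary. The documents give no frequency. Phototherapy is prohibited during the study, so it is probably rare; that is an assumption. The illustrations assume 38 and 19 evaluable participants with complete response data.

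**What to change.** In SAP 8.3, count phototherapy for AD as a systemic SoC event when it appears in any medication or procedure record, whether or not a psoralen is coded. Exempt the phototherapy entry from the route filter. Use the same definition in the set-to-missing step of 8.4.1, which now refers only to medication. Keep the existing rule that SoC begun after discontinuation for other reasons does not trigger non-response.

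This takes about one sentence in 8.3 and a matching phrase in 8.4.1. If phototherapy is recorded as a procedure, there is one more data source to check at blind review, and SAP 6.3 already plans to tabulate it. Sample size, power and clinical rules are unchanged.

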7.2 Participant Discontinuation/Withdrawal from the Study

- A participant may withdraw from the study at any time at the participant's own request, for any reason (or without providing any reason)
- A participant may be withdrawn at any time at the discretion of the investigator for safety, behavioral, compliance, or administrative reasons.
- At the time of discontinuing from the study, if possible, the EOT and FU visits should be conducted, as shown in the SoA (Section 1.3). See SoA for data to be collected at the time of study discontinuation (EOT) and FU and for any further evaluations that need to be completed.
- The participant will be permanently discontinued both from the study intervention and from the study at that time.
- If the participant withdraws consent for disclosure of future information, the sponsor may retain and continue to use any data collected before such a withdrawal of consent.

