9.3.2.1 Primary Efficacy Endpoint

The primary efficacy endpoint is achievement of 75% reduction from baseline in the Eczema Area and Severity Index (EASI 75 response) at Week 12 (Day 84). The EASI score ranges from 0 to 72. The lower the EASI score the better the state of the participant with respect to severity and extent of AD symptoms.

The analysis of the primary efficacy endpoint on the PPS will be performed as follows:

The impact of a potential use of rescue medication (TCSs or TCIs) or SoC for treatment of AD on the efficacy effect will be accounted for as follows:

If rescue medication is used between Day 56 (Visit 6) and Day 84 (Visit 7) or if SoC is used (at any time), the participant will be specified as a non-responder with respect to the EASI 75 response from the time the rescue medication or SoC medication is used.

If a participant discontinues study intervention due to lack of efficacy at any time (e.g., due to an adverse event related to AD such as disease flare), the participant will also be specified as a non-responder with respect to EASI 75 response from the time of the discontinuation.

Otherwise, missing data - e.g. due to study intervention discontinuation due to other reasons such as reasons related to Covid-19 pandemic (individual reasons or prevention/logistic measures), withdrawal of consent not due to lack of efficacy or adverse events not related to AD - will be imputed using a multiple imputation approach based on logistic regression model. Details will be specified in the SAP. Furthermore, alternative imputation methods might also be specified in SAP.

The following supplementary analyses will be performed to further assess rescue medication use. The study participant is considered a non-responder in case of rescue medication use between the EOT visit and

- baseline
- 1 week after baseline,
- 2 weeks after baseline,
- 4 weeks after baseline,
- 6 weeks after baseline.

One additional analysis will be performed where rescue medication does not trigger the classification as non-responder at all to assess the effect of combined treatment of zabedosertib with topical AD medication.

Participants who take SoC medication or who discontinue study intervention due to lack of efficacy will still be counted as a non-responder for the time points after SoC use or discontinuation of study intervention due to lack of efficacy as described above.

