Bayesian inference will be used to quantify the EASI 75 responder rates on Day 84 in the zabedosertib and placebo treatment group. For each treatment group a non-informative Beta(1,1) prior will be used. The Beta(1,1) prior produces a posterior distribution in the same distribution family, namely Beta(k+1,n-k+1) with k being the number of EASI 75 responders in the respective treatment group and n being the number of all participants in the respective treatment group. Simulations based on the posterior distributions of the EASI 75 response rate in both treatment groups will then be used to calculate the posterior probability P($\pi_{BAY} > \pi_{Plac}$ | data). In addition, median and 90% and 95% credible intervals will be calculated based on the posterior distributions for the response rates in both treatment groups as well as for the difference between both treatment groups.

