9.5 Sample Size Determination

A Bayesian concept will be used for inference, which is based on the posterior probability that the research hypothesis is true. Therefore, it is the goal of this study to demonstrate that zabedosertib is superior to placebo with posterior probability > 90%, i.e. $P(\pi_{BAY} > \pi_{Plac} | data) > 90\%$ (='clinical activity' criterion).

The EASI 75 responder rate of 0.49 for assumed systemic standard of care (SoC) dupilumab was derived as the mean responder rate from a meta-analysis on the active treatment arms in two Phase 3 AD studies (Simpson et al, 2017), comprising 919 participants.

Non-informative Beta(1,1) priors will be used for the Bayesian inference. For Placebo, a response rate of 16% was assumed. The statistical power was determined with SAS 9.4. Assuming that the EASI 75 responder rate in zabedosertib-treated participants is 0.49, evaluable data from 57 participants (38 on zabedosertib, 19 on placebo) will provide at least 90% power to establish superiority of zabedosertib. Approximately 72 participants will be randomly assigned to the study to obtain 57 evaluable participants overall (2:1 randomization zabedosertib versus placebo).

10 Supporting documentation and operational considerations

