- Signs, symptoms, or the clinical sequelae of a suspected overdose of either study intervention or a concomitant medication. Overdose per se will not be reported as an AE/SAE unless it is an intentional overdose taken with possible suicidal/self-harming intent. Such overdoses should be reported regardless of sequelae.
- Sign, symptoms, or the clinical sequelae of suspected medication errors, misuse and abuse of either study intervention or a concomitant medication. Medication errors, misuse and abuse per se will not be reported as an AE/SAE, unless it is resulting in AE/SAE. Such medication errors, misuse and abuse should be reported regardless of sequelae.
- Lack of efficacy or failure of expected pharmacological action per se will not be reported as an AE or SAE. Such instances will be captured in the efficacy assessments. However, the signs, symptoms, and/or clinical sequelae resulting from lack of efficacy will be reported as AE or SAE if they fulfill the definition of an AE or SAE.

Events NOT Meeting the AE Definition

- Any abnormal laboratory findings or other abnormal safety assessments that are associated with the underlying disease, unless judged by the investigator to be more severe than expected for the participant's condition
- The disease/disorder being studied or expected progression, signs, or symptoms of the disease/disorder being studied, unless more severe than expected for the participant's condition
- Medical or surgical procedure (e.g., endoscopy, appendectomy): the condition that leads to the procedure is the AE
- Situations in which an untoward medical occurrence did not occur (social and/or convenience admission to a hospital)

• Anticipated day-to-day fluctuations of pre-existing disease(s) or condition(s) present or detected at the start of the study that do not worsen

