4.2.2 Main Analytical Approach

The analysis of the primary efficacy endpoint on the PPS will be performed as follows (according to the primary estimand, refer to Section 1.1):

The impact of a potential use of rescue medication (TCSs or TCIs) or SoC for treatment of AD on the efficacy effect will be accounted for as follows:

If rescue medication is used between Day 56 (Visit 6) and Day 84 (Visit 7) (or end of treatment if before Day 84 (Visit 7)) or if SoC is used (at any time), the participant will be specified as a non-responder with respect to the EASI 75 response from the time the rescue medication or SoC medication is used. SoC medication use after early discontinuation due to other reasons not related to AD will not trigger the classification as non-responder for the following time points.

If a participant discontinues study intervention due to lack of efficacy at any time (e.g., due to an adverse event related to AD such as disease flare), the participant will also be specified as a non-responder with respect to EASI 75 response from the time of the discontinuation.

Otherwise, missing data - e.g. due to study intervention discontinuation due to other reasons such as reasons related to Covid-19 pandemic (individual reasons or prevention/logistic measures), withdrawal of consent not due to lack of efficacy or adverse events not related to AD - will be imputed using a multiple imputation approach based on logistic regression model.

Bayesian inference will be used to quantify the EASI 75 responder rates on Day 84 in the zabedosertib and placebo treatment group. For each treatment group a non-informative Beta(1,1) prior will be used. The Beta(1,1) prior produces a posterior distribution in the same distribution family, namely Beta(k+1,n-k+1) with k being the number of EASI 75 responders in the respective treatment group and n being the number of all participants in the respective treatment groups based on the posterior distributions of the EASI 75 response rate in both treatment groups will then be used to calculate the posterior probability $P(\pi_{BAY} > \pi_{Plac} \mid data)$. In addition, median and 80% and 95% credible intervals will be calculated based on the posterior distributions for the response rates in both treatment groups as well as for the difference between both treatment groups.

Code similar to the following will be used for the Bayesian analysis:

```
data test;
    call streaminit(1234);
    do i=1 to &simno.;

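### SAP 8.3 lists no reason code for participants who withdraw because the drug did not work, so some failures can be excluded or imputed in the primary analysis instead of scored as non-responders

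*SAP*

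**What the plan says.** **Intent.** Protocol 9.3.2.1 sets the rule: "If a participant discontinues study intervention due to lack of efficacy at any time", the participant is a non-responder from then on. SAP 4.2.2 repeats it. Both then describe what is left over as missing data for multiple imputation, and their examples include "withdrawal of consent not due to lack of efficacy". So the plan itself splits consent withdrawals by cause.

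**Operational rule.** SAP 8.3 says that all discontinuation reasons will be reviewed and that the underlying reason decides. It then lists three:

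1. An adverse event that reflects lack of efficacy. Some coded terms always count; the rest are classified in blind review.
2. Lack of efficacy, "based on the investigator's assessment and there is no respective adverse event reported".
3. A physician decision to switch to other therapy, with an instruction on when it should be selected.

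Participant withdrawal is not listed, although Protocol 7.2 lets a participant leave at any time with or without giving a reason. Protocol 10.3.1 adds that signs, symptoms and "clinical sequelae resulting from lack of efficacy will be reported as AE or SAE if they fulfill the definition of an AE or SAE".

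**Consequence of falling outside the list.** Under the primary estimand (SAP 1.1), a stop unrelated to lack of efficacy is excluded if before Day 56 and imputed if at or after Day 56. SAP Section 3 adds that standard-of-care use after such a stop does not restore PPS membership.

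**The concern.** The statement of intent and the operational list do not match. A participant who leaves because the eczema has not improved is a treatment failure under SAP 4.2.2. If the site records the stop as withdrawal by the participant, nothing in the SAP 8.3 list makes it one. The same patient can therefore be a non-responder, absent, or imputed, depending on how the reason was recorded.

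A smaller gap lies in the second listed reason. If lack of efficacy is recorded and an AD-worsening adverse event is also reported, the second reason is closed by its own wording. The first is framed around a recorded reason of adverse event, and the text does not say that the case moves there. Better documentation of the failure should not make its classification less certain.

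Leaving for lack of benefit can depend on treatment. Failures lost unequally between arms would shift the primary posterior probability, which rests on only 57 planned evaluable participants.

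**Working it through.** **Step 1. Trace the cases through the text.**

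| Case | Under SAP 4.2.2 | Under SAP 8.3, read literally | Primary PPS analysis |
|---|---|---|---|
| Coded participant withdrawal, cause lack of efficacy, before Day 56 | Non-responder | No listed reason, so other reasons | Excluded, unless an end-of-treatment or unscheduled EASI falls in the Visit 6 window |
| Same, at or after Day 56 | Non-responder | Other reasons | Multiply imputed if there is no Day 84 value |
| Coded lack of efficacy, with an AD-worsening adverse event | Non-responder | Second reason closed; first not stated to apply | Unclear |
| Coded lack of efficacy, with an unrelated adverse event only | Non-responder | Second reason applies | Non-responder |

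The window exception comes from SAP 8.4.1. An early end-of-treatment EASI taken within three days of the last dose is assigned to Visit 6 if it falls on Days 49–63, and to Visit 7 on Days 76–92.

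**Step 2. Inputs for sizing.** From Protocol 9.3.2.1: "For each treatment group a non-informative Beta(1,1) prior will be used". From Protocol 9.5: success if P(π_BAY > π_Plac | data) > 0.90; 38 and 19 evaluable; zabedosertib rate 0.49; "For Placebo, a response rate of 16% was assumed". The number of misrouted failures is not given, so I assume 0 to 4 per arm. The plan allows 72 − 57 = 15 non-evaluable participants for all causes.

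**Step 3. Formula.** With k responders of n in an arm, the posterior is Beta(k+1, n−k+1). Then P = ∫ f_BAY(x) F_Plac(x) dx, computed by numerical integration. Power is the sum of binomial probabilities over all outcome pairs with P > 0.90.

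**Step 4. Reproduce the plan's figure.** At 0.49 vs 0.16 with 38 and 19, exact power is 91.0%, in line with the stated minimum of 90%. At 0.16 in both arms, the criterion is met 6.9% of the time.

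**Step 5. Borderline results.**

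| Analysed | P | Compared with | P |
|---|---|---|---|
| 12/38 vs 3/19 | 0.885, missed | one placebo failure restored: 12/38 vs 3/20 | 0.903, met |
| 13/38 vs 3/19 | 0.918, met | two placebo failures dropped: 13/38 vs 3/17 | 0.879, missed |
| 12/38 vs 3/19 | 0.885, missed | two active failures dropped: 12/36 vs 3/19 | 0.906, met |
| 13/38 vs 3/19 | 0.918, met | two active and one placebo dropped: 13/36 vs 3/18 | 0.921, met |
| 12/38 vs 3/19 | 0.885, missed | two active and one placebo dropped: 12/36 vs 3/18 | 0.888, missed |

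Near the design assumption nothing changes: 19/38 vs 3/19 gives 0.994, and vs 3/17 gives 0.987.

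**Step 6. Operating characteristics when failures are dropped from full arms of 38 and 19.**

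| Dropped (active, placebo) | Criterion met at 0.16 vs 0.16 | Power at 0.49 vs 0.16 |
|---|---|---|
| 0, 0 | 6.9% | 91.0% |
| 2, 0 | 10.0% | 92.4% |
| 0, 2 | 5.4% | 83.5% |
| 4, 2 | 7.8% | 91.1% |

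Losing active failures favours zabedosertib, losing placebo failures works against it, and loss in the 2:1 ratio nearly cancels.

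**The case against.** The strongest reply is that SAP 8.3 looks at the underlying reason, that all reasons are reviewed, and that an investigator may record lack of efficacy for a participant who leaves because the drug failed. SAP 4.2.2 already states the governing principle. The case report form's list of reasons is not in the documents, and the detailed imputation text is redacted; neither counts against the plan. This weakens any claim that such a participant can never be classified correctly. It does not close the gap. Section 8.3 gives no rule for recoding a withdrawal, and the blind classification it describes for stops covers only adverse events leading to discontinuation.

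Three stronger readings are tempting, and the documents do not support them.

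- *Any adverse event closes the lack-of-efficacy reason.* Only a respective event does, meaning one that expresses the lack of efficacy. Such cases are evidently meant for the first reason, where flare, aggravation and rebound terms always count. What remains is that the text does not say so, and that other terms depend on blind classification.
- *The full analysis set (FAS) repeats the problem.* FAS analyses B_6.1 and B_7.1 score other-reasons stops as non-response, given a valid EASI at Day 14 or later. Within the PPS, B_1.2 scores missing Day 84 responses the same way. But B_1.2 cannot recover anyone already excluded, and none of these is the primary analysis.
- *Every misrouted failure is lost.* AD-related standard of care before stopping, or AD-related rescue from Day 56 while on treatment, still makes the participant a non-responder. Imputation uses baseline and Day 56 EASI, so an unimproved patient would probably be imputed mostly as a non-responder.

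**Conclusion.** The point holds in a limited form. The SAP 8.3 list is narrower than the rule it is meant to apply. Read literally, it can move a failing participant coded as a withdrawal out of the non-responder category in the primary analysis, contrary to the plan's own estimand. The wording on lack of efficacy with a respective adverse event is a lesser ambiguity of the same kind.

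The size is uncertain because the documents give no count of such withdrawals. One or two cases in a single arm matter only when the posterior is already close to 0.90. A reader might infer from the reversals that the trial's conclusion is generally fragile, or that the bias favours zabedosertib. Neither follows: the reversals shown have borderline counts with all the loss in one arm, the direction depends on that arm, and loss in proportion to allocation leaves both error rates almost unchanged. These figures assume independent binomial outcomes at the planned sample size, and treat misrouted failures as dropped rather than imputed.

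The change is worth making because it concerns the primary endpoint, costs little, and can be settled before unblinding.

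**What to change.** Amend SAP 8.3 in two places.

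1. State that a recorded reason of lack of efficacy counts whether or not a respective adverse event is reported, by deleting the adverse-event clause from the second reason.
2. Add that a participant withdrawal, or another physician decision, counts as this event when the reason text already documented, or an AD-worsening adverse event leading to the stop, shows lack of efficacy. Decide these cases in the planned blind review, by persons without access to individual post-dose efficacy data.

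Two further steps are not recommended. A new question to sites on whether lack of efficacy contributed to each stop would be mostly retrospective: SAP 4.7 puts about 90% of participants as randomized by 02 August 2023, 84 days from then is 25 October, and the SAP is dated 31 October 2023. Using AD treatment started at the stop as evidence would conflict with the SAP's rule that standard-of-care use after an other-reasons stop does not trigger non-response.

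The cost is a few lines of SAP text and a few more blind-review decisions. No participants, visits or data collection are added.
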